Data capture will be facilitated by the use of the REDCap Clinical Data Interoperability Services (CDIS) tools. Project team members listed as Key Study Personnel with existing electronic health record (EHR) system access rights will make use of REDCap CDIS tools. These tools are designed to enable transfer of relevant study-related data from the Vanderbilt Research Derivative and/or directly from the EHR into REDCap.

Primary Outcome:

The highest level of support on the 5th day after enrollment according to the following scale adjusted for patient status at enrollment according to the same scale and ranked by mean FIO₂ within each category, as appropriate.

- Death
- ECMO
- Mechanical ventilation (ranked by mean FIO₂)
- Non-invasive ventilation such as BiPAP (ranked by mean FIO₂)
- High flow nasal cannula, e.g. Optiflow, Vapotherm or other similar device (titrated by FIO₂%) (ranked by mean FIO₂)
- Standard nasal cannula (titrated by L/min up to 15 L/min) or face mask (ranked by mean FIO₂)
- Room air

Notes:

- The **mean** value of FIO₂ as a weighted average on day 5 is used for outcome assignment ranking.
- FIO₂ on standard nasal cannula or face mask is estimated as 21 + 3 x liters per minute (LPM) O₂ flow.
- Non-rebreather face mask is highest (worst) rank within the standard nasal cannula or face mask category.

Study Protocol: Version 7.0 - October 29, 2020

Full Study Title: Pragmatic Trial Exploring Impact of Patient Positioning in the Management of Patients Infected with COVID19: Supine vs. Prone

Primary Investigator: [name], MSc

- FIO₂ on high flow nasal cannula, e.g. Optiflow, Vapotherm or other similar device is estimated as the %FIO₂ on the machine.
- For patients who are discharged or lost to follow up before day 5, the last documented modality and FIO₂ will be carried forward.

Secondary Outcomes:

For each day, we will record the most intensive oxygen delivery mode and then, for that highest level of oxygen support device, the max FiO₂ while exposed to that device.

3. Inclusion/Exclusion Criteria

Inclusion:

- This study will enroll COVID-19 positive patients admitted to VUMC who require supplemental oxygen, who have yet to be placed on mechanical ventilation during their hospitalization. We will use the hospital's operational status definition to identify COVID-positive case status.

Exclusion:

- Per above, patients admitted on mechanical ventilation will be excluded from enrollment.

4. Enrollment/Randomization

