Regulatory Considerations:

This study is seeking a waiver of informed consent. The study is believed to be minimal risk as patients naturally orient themselves in both supine and prone positioning. There is no current evidence to support that the prone or supine position is superior in alleviating symptom progression in this disease state, demonstrating equipoise between groups. The rights and welfare of participants are not adversely affected by this study, as this is something they would normally encounter in usual care. The addition of a sensor to monitor patients is common practice, and the readout here will document patient positioning choice (15,16). Within the subset to be monitored for protocol fidelity, patient assent will be obtained. Moreover, the request for positioning and device monitoring still allows the patient to maintain autonomy. Providers are also freely able to adjust the positioning of the patient as they see fit. It is impracticable to fully consent patients for this study as this would introduce bias. Making patients aware of prone positioning may encourage supine patients to assume a prone position, when they would not usually do so.

7. Study Withdrawal/Discontinuation

Patients will not generally have the option to self-withdraw from the study, however, physicians retain the right to discontinue upon unacceptable patient decompensation.

8. Statistical Considerations

The majority of clinical trials in COVID-19 are using the WHO ordinal outcome scale, or some adaptation thereof. This outcome scale differentiates patients based on their need for supplemental oxygen or, if they are not using oxygen, whether they need help or support for activities of daily living. We have adapted this scale for use in this trial. The adaptation, which involves ranking patients within the ordinal categories based on the magnitude of oxygen requirements, adds granularity to the scale and is intended to increase power. We expect prone positioning to have beneficial effects within the ordinal categories, as well as influencing the method of delivering oxygen (e.g. room air, nasal cannula, high flow nasal cannula, intubation).

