The primary endpoint as an ordinal variable that quantifies provision of oxygen as the main measure of clinical status measured on the fifth day of enrollment. The basis of the outcome is the World Health Organization Ordinal Covid-19 Outcome Scale, and this has been combined with data concerning the intensity of oxygen requirements. Patients are first ranked by categories of oxygenation strategies from the least invasive to the most invasive. Then, within rank, they are assigned a score based on the oxygen delivery settings as follows:

- Death
- ECMO
- Mechanical ventilation (ranked by mean FIO₂ for the day)
- Non-invasive ventilation such as BIPAP (ranked by mean FIO₂ for the day)
- High flow nasal cannula (ranked by mean FIO₂ for the day, estimated from the %FIO₂ recorded on the device)
- Standard nasal cannula (ranked by mean FIO₂ for the day, FIO₂ on standard nasal cannula or face mask is estimated as $21 + 3 \times$ liters per minute (LPM) O₂ flow)
- Room air

To minimize missingness on this primary outcome, we use the approach of last value carried forward for patients who are not observed for the full five days. Patients discharged home are at the bottom end of the scale (generally room air) while those who die will be scored the worst possible outcome. Patients discharged to a long-term care facility or similar have their oxygen needs at transfer recorded as their final requirements. Not many patients are expected in this category because the endpoint is being measured relatively close in time to the intervention (5 days), and when transfers occur in this population, they are likely to occur after much later in the clinical course.

Secondary Endpoints:

The secondary endpoint is constructed the same way as the primary endpoint, but measured on each of the first five days of randomization.

Exploratory Endpoints:

A number of exploratory endpoints have been proposed for this trial, and additional outcome may be proposed as understanding of the underlying disease and treatment course evolves. Below, we list the pre specified exploratory outcomes. For newly proposed endpoints, the analytical approaches will generally be similar to those described below.

- Length of Stay
- ICU Length of Stay
- Intubation yes/no

- Ventilator-free days (VFDs) to 28 days, calculated as a backwards count of whole days from day 28 to the last day in receipt of mechanical ventilation.
- Oxygen Levels
 - Maximum FIO2 for each day 1-5 after enrollment

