and by group. Groups will not be formally compared used statistical tests; differences and confidence intervals of differences may be reported. All categorical variables will be described using frequencies and proportions, and continuous variables will be described using mean, standard deviation, and percentiles (i.e. 25th , 50th , 75th). Missingness will be recorded for each variable. To further assess the distribution of variables, graphical summaries will be displayed using box-plots, dot-plots, violin-plots, and/or histograms. At a minimum, the following baseline variables will be described:

- Age (years)
- Sex (Male, Female, Not reported)
- BMI – kg/m²
 - Obesity (None, Stage I BMI 30.0 -34.9; Stage II BMI 35.0 – 39.9; Stage III BMI>=40.0, Not reported)
- Race (American Indian/Alaska Native, Asian, Black/African American, White, Other, Not reported)
- Ethnicity (Hispanic or Latino, Not Hispanic or Latino, Not reported)
 - Ethnicity may be combined with race
- Elixhauser Score
- Number of coexisting conditions (None; One; Two or more)
- Coexisting conditions (Yes/No)
 - Any
 - Diabetes
 - Hypertension
 - Underlying Respiratory Disease
 - Heart Disease
 - Renal Disease
 - Malignancies
- Smoking Status (as documented in the EMR)
- Renal replacement therapy required at enrollment (Yes/No)
- Vasopressors required at enrollment (Yes/No)
- Score on ordinal scale at enrollment (Hospitalized on low flow supplemental oxygen; Hospitalized on high flow supplemental oxygen; Hospitalized on non-invasive ventilation)

Subsequent to characterizing the cohort at baseline, we will explore and describe the outcome variables overall and grouped by study arm. We will take the same approach as for the cohort descriptors, using comprehensive summary statistics and graphical representations as appropriate. For depicting clinical course, alluvial or Sankey plots maybe be used.

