We will describe fidelity of the intervention using the ‘dose’ of proning. This will be characterized primarily using nursing estimates of the number of hours a patient spent prone during a shift. Briefly, each nursing shift lasts for 12 hours, running from 7am to 7pm. After each shift, the nurse was asked to estimate for how many hours enrolled participants were prone, regardless of which study arm they were in. We will characterize the time spent prone as estimated total time, proportion of time, average time per shift. We note that a supplementary study included more formal objective measurements of proning. The accuracy of the nursing estimate of proning may be estimable and reported as a result of that supplementary study.

Main Analysis

Our main analysis will be a covariate-adjusted proportional odds (PO) regression model with the main predictor being group assignment. Suppose the outcome Y_i for participant i can take one of the J ordered level of responses $j = 1, 2; \dots; J$. The PO logistic regression models the logit as a linear function of the randomization groups and a set of pre-specified covariates:

$$\text{Log} \left(\frac{\Pr(Y \leq j)}{1 - \Pr(Y \leq j)} \right) = \alpha_j + \beta_1 X_1 + \dots + \beta_p X_p, \quad \text{for } j = 1, 2, \dots, J - 1 \quad (1)$$

where X_1 is an indicator variable that defines the treatment groups, X_2 represents the important baseline covariate of severity, and the remaining X_s represent the additional covariates.

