In the proportional odds model we assume that the relationship between each level in the outcome variable is proportional, so the effect that describes the relationship between the lowest category versus all higher categories of the outcome variable is the same as the relationship that describes the next lowest category and all higher categories. The proportionality assumptions will be explored graphically e.g. the logit of the empirical cumulative distribution function of the outcome should be parallel among categories of covariate X_j , and a partially proportional odds model may be pursued. The covariates that will be included in the model are those listed in the descriptive analyses, which include the important variable of baseline severity. Duplication of comorbidity variables will be avoided; only the Elixhauser score will be used. To check other model assumptions, the approaches described in Regression Modeling Strategies (Harrell 2015, 2nd ed.) will be used, i.e. we will assess the model fits, residual plots, partial effect plots, and/or anova plots (Wald minus the d.f.) will be displayed. Model results will be summarized with point estimates, 95% C.I., and p-values displayed in tabular form or graphically, along with model fit statistics.

Secondary Analysis

We have specified a single primary endpoint, and so we are not adjusting for multiplicity. Since our secondary endpoint should be more sensitive than the primary for changes in the outcomes, we are not employing a gatekeeping strategy. We will proceed with the secondary analysis regardless. With up to 5 outcome measurements per patient, a proportional odds model will be specified to include the random effect of patient and we will include number of days since enrollment. We will additionally include the time by treatment interaction to determine whether there is a differential treatment effect of proning over the observational window.

For exploratory outcomes, binary outcomes will be modeled assuming a logit link function, and ordinal and discrete outcomes will be modeled using a proportional odds model. Similar approaches will be used to modeling as for the main analyses.

Missingness

We do not expect missingness on our primary outcome. There may be missingness on covariates or on secondary or exploratory outcomes. We will not exclude cases with missing covariates. We will use multiple imputation with predicted mean matching. Cases with missing outcomes may also have the outcomes imputed

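### As written, the SAP codes baseline severity in the primary model as three device levels without FIO2; a coding as fine as the outcome would be a cheap efficiency gain

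*SAP*

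**What the plan says.** The SAP's Main Analysis gives a proportional odds model in which X1 is treatment and X2 "represents the important baseline covariate of severity". X2 gets no further coding there. The covariates are then fixed by reference: "The covariates that will be included in the model are those listed in the descriptive analyses, which include the important variable of baseline severity".

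The list meant is in the SAP's Descriptive Analysis, introduced by "At a minimum, the following baseline variables will be described". Its one oxygen-severity entry is "Score on ordinal scale at enrollment (Hospitalized on low flow supplemental oxygen; Hospitalized on high flow supplemental oxygen; Hospitalized on non-invasive ventilation". BMI appears there both as a measured value and as obesity groups; severity appears as groups only.

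The outcome is finer. After ranking by device, the SAP's Primary Endpoint section adds: "Then, within rank, they are assigned a score based on the oxygen delivery settings as follows". Protocol section 8 explains why: "ranking patients within the ordinal categories based on the magnitude of oxygen requirements, adds granularity to the scale and is intended to increase power".

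Protocol section 2 defines the primary outcome as "adjusted for patient status at enrollment according to the same scale". Section 8 then frames the question as a comparison of two patients with equal oxygen needs at baseline.

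**The concern.** The within-device detail is applied to the outcome but, on the reading the SAP text leads to, not to the covariate meant to explain most of that outcome. Two consequences follow if FIO2 within device predicts day-5 status.

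- **Power.** The three-level model estimates a conditional odds ratio nearer to 1 with almost the same standard error, so it has somewhat less power.
- **Question answered.** It compares patients on the same device, not patients with the same oxygen requirement, which is what protocol section 8 asks.

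No type I error problem is at stake, and the stated power is not claimed to be missed.

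**Working it through.** **What three levels merge.** Protocol section 2 estimates low-flow FIO2 as 21 + 3 × L/min, for flows up to 15 L/min. At 1 L/min this is 21 + 3 × 1 = 24%; at 15 L/min it is 21 + 3 × 15 = 66%. On day 5 these patients are ranked apart. At baseline they share one code.

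**Reproducing N = 500.** Whitehead's formula, 1:1, OR 1.6, 80% power, two-sided 5% (alpha is not stated; assumed from the 95% intervals):

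N = 12 (1.960 + 0.842)² / [(ln 1.6)² (1 − Σp³)] ≈ 426 / (1 − Σp³)

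The interim distribution is not given, so p comes from the distribution in protocol section 8.

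- Six listed categories, control arm: Σp³ = 0.095, N = 471. Averaged over arms, N = 484 (81.2% power at 500).
- Room air pooled at 40 + 10 = 50%, five categories, control arm: Σp³ = 0.155, N = 504.
- Room air pooled and 22 FIO2-graded ranks, averaged over arms: N = 516 (78.7% power at 500).

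The stated 500 therefore fits an unadjusted OR of 1.6, although the documents do not say so.

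**Efficiency check.** From the documents: N = 500, OR 1.6, and day-5 control proportions of 50% room air, 30% low flow, 14% high flow or non-invasive ventilation (HF/NIV), 5% ventilated, 1% death. Assumed:

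- baseline device mix 82/14/4% or 70/24/6%, with device odds ratios 4 and 8 against low flow;
- low flow of 1-15 L/min, mean 4.0, SD 3.1;
- prognostic age, BMI and Elixhauser score, plus seven null terms, in every adjusted model.

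The unknown is the odds ratio per SD of FIO2 within device. From 1 to 15 L/min is 14 / 3.1 = 4.52 SD, so 1.25, 1.5 and 2.0 per SD imply 1.25^4.52 = 2.7, 1.5^4.52 = 6.2 and 2.0^4.52 = 22.9-fold odds. For that reason 2.0 is treated as the upper end.

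Model A has treatment, three device levels and the other covariates. Model B adds linear FIO2 slopes in low flow and in HF/NIV (2 df). Model C uses a 3-knot spline in low flow and a linear slope in HF/NIV (3 df). Effective sample size ratio = (β/SE)² for B divided by (β/SE)² for A, from fits to 300,000 records scaled to N = 500.

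Reading 1 takes 1.6 as the unadjusted odds ratio; reading 2 takes it as the conditional one. The noisy columns assume reliability 0.7. Power is for the 82/14/4% mix.

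| OR per SD | Effective N gained | Gained, noisy | Power, reading 1, A → B | Reading 1, noisy | Power, reading 2, A → B |
|---|---|---|---|---|---|
| 1.0 | 0% | 0% | 86.0 → 86.0% | 86.1 → 86.2% | 76.2 → 76.2% |
| 1.25 | 1.5-1.6% | 0.9-1.0% | 86.3 → 86.8% | 86.5 → 86.8% | 75.5 → 76.2% |
| 1.5 | 5.1-5.3% | 3.1-3.2% | 86.5 → 88.1% | 86.6 → 87.7% | 73.5 → 75.6% |
| 2.0 | 15.0-16.1% | 9.1-9.3% | 86.6 → 91.0% | 86.7 → 89.4% | 67.6 → 74.0% |

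Worked line (OR 1.5, reading 1): 86.5% power is z = 1.960 + 1.103 = 3.063. Then 3.063² × 1.051 = 9.86, whose root is 3.140, and Φ(3.140 − 1.960) = 88.1%. At this setting the standard error is 0.178 in A and 0.180 in B, so the gain comes from an estimate further from 1. Model C is within 0.001 of B on the ratio.

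**Second check, different assumptions.** A simulation at N = 500 indexed by the within-device correlation r between baseline FIO2 and the latent day-5 outcome gives relative efficiency 1.00, 1.03, 1.08-1.09 and 1.16-1.17 at r = 0, 0.2, 0.3 and 0.4. With r = ln OR / √((ln OR)² + 3.29), odds ratios 1.25, 1.5 and 2.0 correspond to r of about 0.12, 0.22 and 0.36, so the two checks broadly agree.

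**Cost when FIO2 is not prognostic.** In 2,000 simulated trials of N = 500 (reliability 0.7, reading 1), A and C had power 87.2% and 87.3%. At OR 1.5 it was 88.2% and 88.5%; at 2.0, 88.4% and 90.3%. Null rejection across these settings was 4.0-4.8% for A and 4.6-5.1% for C.

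**The case against.** The counter-case has real substance.

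- **The three-level coding is inferred.** The list is a minimum for description, its brackets may only be table categories, and the Main Analysis itself overrides the list by keeping only the Elixhauser score for comorbidity. This stands, which is why the point is put as written. It does not remove the problem: no finer coding is specified, and the SAP says it aims to let an independent statistician follow the approach.
- **The protocol is not fully explicit.** Its phrase on ranking by mean FIO2 may belong to the day-5 outcome only. This also stands, but same-scale adjustment and the section 8 question both favour finer coding.
- **The size is assumed and mostly small.** With a noisy value at N = 500 the simulated power gains are 0.1, 0.3 and 1.9 points at OR 1.0, 1.5 and 2.0, against a Monte Carlo standard error near 0.7 points for each figure. No figure here can be taken from the documents, and a large benefit appears only at the upper end.
- **The remedy is not exactly the outcome's scale.** A single baseline value is not a day mean, and giving non-rebreather masks a numeric value turns a rank rule into a number. Both are compromises to be stated openly.
- **Timing.** The SAP is dated 9 January 2021 and describes the second site's contribution in the past tense. Whether the model can still be changed before unblinding is unknown.

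**Conclusion.** The point holds as a cheap improvement, not an error. As written, X2 is a three-level device score, coarser than the outcome and than the adjustment the protocol describes. Adjusting on it is valid. Finer coding gains nothing if FIO2 within device is not prognostic. At OR 1.5 per SD it gains about 5% in effective sample size (0.051 × 500 to 0.053 × 500, about 26 patients). At OR 2.0, the upper end, it gains 15.0-16.1% (75 to 81 patients). With reliability 0.7 these fall to 3.1-3.2% and 9.1-9.3%. The gains rest on the assumed prognostic strength, device mix and flow distribution, so confidence in the size is medium. The mismatch with the protocol's question does not depend on those assumptions.

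**What to change.** Before the arms are unblinded for analysis, amend the SAP's Main Analysis as follows.

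1. Define X2 as enrolment device category plus FIO2 within device, with a stated form: for example a 3-knot restricted cubic spline for low flow and a linear slope for high flow and non-invasive ventilation.
2. Keep the device terms. Replacing them with one splined rank score cost 1-2% of effective sample size when FIO2 was not prognostic (ratio 0.980-0.988).
3. Use the protocol's low-flow formula. Place non-rebreather masks at the worst low-flow value, following the protocol's rule: "Non-rebreather face mask is highest (worst) rank within the standard nasal cannula or face mask category".
4. Use the last value documented at or before enrolment. Enrolment is the anchor because MRN parity fixes the arm beforehand (protocol section 4). State that this differs from the outcome's day mean: day zero is the day of assignment (section 5), so its mean could include time after the intervention starts.
5. Put missing values into the planned multiple imputation, and keep the three levels for the descriptive table.
6. If three levels are intended, say so and reconcile this with protocol sections 2 and 8.

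The cost is SAP wording, 2-3 degrees of freedom and one record value per patient at both sites.
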